#### 8.3.5.5 Sensitivity and Supporting Analyses

A dropout rate of 20-30% is typically seen in MDD studies. Subjects will be grouped by the visit at which they had their last MADRS total score measured. This will result in five categories of discontinuation: Week 1 dropouts, Week 2 dropouts, Week 3 dropouts, Week 4 dropouts, and completers. Mean change from Baseline in MADRS total score will be plotted by the dropout category and by reason for discontinuation, to assess whether this efficacy measure appears to be correlated with study dropout.

The mechanisms that cause missing data may be missing at random (MAR) or may be missing not at random (MNAR). The MMRM model (as implemented within the PROC MIXED procedure in SAS) used in the primary analysis of the primary efficacy endpoint relies on the assumption of MAR.

Therefore, a sensitivity analysis using the tipping-point approach may be used to assess the robustness of the primary analysis approach, in the event the primary analysis is positive. Missing data are first imputed for all visits under the missing-at-random (MAR) assumption, and then a worsening/shift is applied. This is repeated until the result is no longer statistically significant (i.e., p>0.05). The tipping point (smallest worsening/shift in which the significant result turns non-significant) provides a measure of robustness of the primary result. Additionally, in the event the primary analysis is positive a multiple

Form STAT401.V3 Page 13 of 23

Client/Project	Arrivo/Sirtsei 201
Version and Date	V01 August 26, 2022

imputation analysis will be performed with 100 imputations of the study data using available results and variables used in the primary analysis (week, treatment, week to treatment interaction, and baseline MADRS score) to model missing data for each treatment group. Each imputed dataset will be analyzed separately using the same MMRM model in the primary efficacy analysis. The estimates from the imputed model analyses will be combined for statistical inference.

#### 8.3.5.6 Covariate and Other Supporting Analyses

The mean change from baseline in total MADRS total score after 4 weeks of treatment between treatment groups will be compared using the same MMRM model as the primary efficacy analysis but with age added to the model as a covariate analysis.

A primary concern for this study is the homogeneity of treatment groups across sites. A test for homogeneity using the same MMRM model as the primary efficacy analysis will be used with site and the interaction of site by treatment added as fixed effects. Sites with less than 10 subjects will be pooled to obtain at least 10 subjects. Sites will be pooled in order of site number. The last un-pooled site will be pooled with the last set of sites pooled if the site has less than 10 subjects.

#### 8.3.6 Secondary Efficacy Endpoints

Seven secondary efficacy endpoints will be analyzed using the mITT populations. Where a model similar to the primary analysis is identified, the model may be reduced, if necessary, for convergence issues. These will be supported by descriptive summaries of results by group. These include:

- Change from Baseline to Weeks 1, 2, and 3 in MADRS total score for SP-624 vs. placebo. The outcome will be analyzed using the same methods as the primary outcome using estimate statement statements for each timepoint from the overall model.
- CGI-S is measured on a 7-point scale where 1 represents "normal" and 7 represents "most extremely ill". A summary of percentage of subjects with each score at Baseline and at Weeks 1, 2, 3, and 4 will be presented. The change from Baseline in CGI-S can take on interval values between -6 (improvement from 7 to 1) and 6 (worsening from 1 to 7). Treatment comparison of change from Baseline to Weeks 1, 2, 3, and 4 in CGI-S scores will be performed using an MMRM model similar to that of the primary efficacy variable.
- Change from Baseline to Week 5/1-Week Follow-up and change from Week 4 to Week 5 will be assessed for the MADRS and CGI-S. Treatment comparisons will be performed using an MMRM model similar to that of the primary efficacy variable.
- The HAM-D-17 is a 17-item scale whose total score can range from 0 to 52. Change from Baseline to Week 2 and Week 4 in the 17-item Hamilton Depression Rating Scale (HAM-D-17) total score will be assessed for treatment differences using an MMRM model similar to that of the primary efficacy variable.
- The Sheehan Disability Scale (SDS) is a 3-part scale that measures the degree of disruption on work, social and family life using an 11-point scale where 0 represents "no disruption" and 10 represents "extreme disruption". In addition to the 11-point scale, subjects are asked to indicate the number of days in the past week that were "lost" and numbers of days that were "unproductive". The results of these questions have a range from 0 to 7. A total global functioning impairment score can be utilized by summing the scores from work, social and family life scales for a value range from 0 to 30. Treatment difference in change from Baseline to Week 2 and Week 4 for both global functioning impairment and days lost/unproductive will be assessed using an MMRM model similar to that of the primary efficacy variable. Change in days lost will be analyzed separately from change in unproductive days.
- The Quick Inventory of Depressive Symptomology Self Report (QIDS-SR), is a 16-item self-reported scale where each item has a 4-point scale where 0 represents least impact scores while 3 represents greatest impact scores. Scale 6 and 7 are linked such that only one of these will be

Form STAT401.V3 Page 14 of 23

Client/Project	Arrivo/Sirtsei 201
Version and Date	V01 August 26, 2022

scored. Likewise, scales 8 and 9 are linked such that only one of them will be scored. Nine domains are scored based on the highest score of items within that domain. The total score from all domains can take a value ranging from 0 to 27. Treatment difference in change from Baseline to Week 2 and Week 4 in the QIDS-SR will be assessed using an MMRM model similar to that of the primary efficacy variable.

• The Quality of Life Enjoyment and Satisfaction Questionnaire – Short Form (Q-LES-Q-SF) is a 16-item satisfaction scale where each item has a 5-point scale. A score of 1 represents "very poor satisfaction", while a score of 5 represents "very good satisfaction". Only the first 14 items are summed for a total score that ranges from 14 to 70 and is expressed as a percentage based on the maximum total score of the items completed (0–100). Treatment difference in the change from Baseline to Week 2 and Week 4 in total scores will be assessed using an MMRM model similar to that of the primary efficacy variable. The last two items pertaining to satisfaction with medications and overall contentment will be summarized separately by treatment group.

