7.2.4.6. Quality of Life Enjoyment and Satisfaction Questionnaire – Short Form

The Q-LES-Q-SF is a subject-completed 16-item questionnaire that assesses life satisfaction over the past week ([Appendix F](#)). Each question is rated on a 5-point scale from 1 (Very Poor) to 5 (Very Good).

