- The Quick Inventory of Depressive Symptomology – Self Report (QIDS-SR), is a 16-item self-reported scale where each item has a 4-point scale where 0 represents least impact scores while 3 represents greatest impact scores. Scale 6 and 7 are linked such that only one of these will be scored. Likewise, scales 8 and 9 are linked such that only one of them will be scored. Nine domains are scored based on the highest score of items within that domain. The total score from all domains can take a value ranging from 0 to 27. Treatment difference in change from Baseline to Week 2 and Week 4 in the QIDS-SR will be assessed using an MMRM model similar to that of the primary efficacy variable.
- The Quality of Life Enjoyment and Satisfaction Questionnaire – Short Form (Q-LES-Q-SF) is a 16-item satisfaction scale where each item has a 5-point scale. A score of 1 represents “very poor satisfaction”, while a score of 5 represents “very good satisfaction”. Only the first 14 items are summed for a total score that ranges from 14 to 70 and is expressed as a percentage based on the maximum total score of the items completed (0–100). Treatment difference in the change from Baseline to Week 2 and Week 4 in total scores will be assessed using an MMRM model similar to that of the primary efficacy variable. The last two items pertaining to satisfaction with medications and overall contentment will be summarized separately by treatment group.

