#### 8.3.6.1 Handling of Missing Items Within a Clinical Assessment

The final scores of the Q-LES-Q-SF, QIDS-SR and SDS are all constructed from multiple sub-questions within each assessment. It is possible that one or more sub-questions may be missing within each assessment. In this event, the last recorded score for this sub-question(s) may be carried forward from the most recent post-dose visit (Last Observation Carried Forward approach). In a similar fashion, missing baseline values may be carried over from the most recent screening visit, if available. Baseline/screening values will never be carried forward to impute missing post-dose values. An individual sub-question will not be carried forward for more than one visit. If the same sub-question is missing two visits in a row, then LOCF will be applied to the first missing visit and the sub-question will remain as missing for the second visit (with the total score to then be computed as missing). Further, the total score will be computed as missing if too many sub-questions, prior to applying the LOCF approach, are missing (>50%). This single imputation approach allows the total score to be calculated using the strength of the other sub-questions collected at that time, for that subject. The Sponsor believes this approach to be more accurate than either setting the entire score to missing or to imputing the worst possible score.

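### The Q-LES-Q-SF formula gives 20–100, not the stated 0–100, and SAP 8.3.6 and 8.3.6.1 handle some blank items differently with no rule of precedence

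*SAP*

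**What the plan says.** Protocol 7.2.4.6 describes the item scale: "Each question is rated on a 5-point scale from 1 (Very Poor) to 5 (Very Good"). SAP 8.3.6 then sums the first 14 items into a total that "ranges from 14 to 70 and is expressed as a percentage based on the maximum total score of the items completed", with the range given as 0–100. Protocol 9.3.4.2 uses the same rule and the same range: it "is expressed as a percentage based on the maximum total score of the items completed (0–100"). Neither document mentions subtracting the minimum. Both say that the change in total scores goes into the MMRM, without saying whether that means the raw sum or the percentage.

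SAP 8.3.6.1 names the Q-LES-Q-SF among the scales covered by its missing-item rule:

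- A blank item may take its value from the most recent post-dose visit, for one visit only.
- A blank baseline item may take a screening value, if there is one.
- "Baseline/screening values will never be carried forward to impute missing post-dose values".
- If the same item is blank at two visits in a row, it stays blank at the second, "with the total score to then be computed as missing".
- The total is also missing if more than 50% of items are blank before any carry-forward.

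The Schedule of Events collects the scale at Baseline, Week 2 and Week 4 only. Sections 8.3.6 and 8.3.6.1 do not refer to each other on this scale.

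**The concern.** A scoring rule and its stated range should agree. Here a programmer who follows the words and one who follows the range produce different numbers from the same forms, and a reader of the tables cannot tell which scale the effect is on.

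The second problem is that two missing-item rules apply to one scale and neither is given priority. Dividing by the maximum of the completed items is already a way of handling blanks. Carrying an item forward, or setting the total to missing, is another. Where they disagree, the programmer's choice affects which visit scores enter the model and what their values are. Where 8.3.6.1 has no instruction that can be carried out, the programmer must decide whether the completed-items rule applies.

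**Working it through.** **1. The stated range**

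Inputs: items score 1 to 5 (protocol 7.2.4.6); 14 items, raw sum 14 to 70, percentage of the maximum of the items completed, stated range 0–100 (SAP 8.3.6; protocol 9.3.4.2). Let n be the number of the 14 items completed.

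- As worded: P = 100 × sum/(5n). With n = 14, the floor is 14/70 = 20% and the ceiling 70/70 = 100%. The floor is also 20% for n = 13 (13/65), n = 10 (10/50) and n = 7 (7/35), because each item's minimum is one fifth of its maximum. The plan's 0–100 is not reproduced.
- With the minimum subtracted: M = 100 × (sum − n)/(4n). With n = 14, this runs from (14 − 14)/56 = 0 to (70 − 14)/56 = 100%. The plan's 0–100 is reproduced.

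**2. Size of the difference**

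- One raw point is 100/70 = 1.43 points on P and 100/56 = 1.79 on M; the ratio is 56/70 = 0.80.
- A 10-point raw gain is 14.3 on P and 17.9 on M.
- For any n, M = 1.25 × P − 25. Changes on M are therefore always 1.25 times changes on P, and MMRM p-values and standardized effects are the same on either scale.

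**3. The two missing-item rules, case by case**

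| Blank item | SAP 8.3.6 | SAP 8.3.6.1 |
|---|---|---|
| Baseline only | scored over 13 items | only donor is Screening, where the scale is not collected; no usable rule |
| Week 2 only | scored over 13 items | only earlier answer is Baseline, which is barred; no usable rule |
| Week 4 only | scored over 13 items | Week 2 answer may be carried forward |
| Same item, Baseline and Week 2 | Week 2 scored over 13 items | Week 2 total missing |
| Same item, Week 2 and Week 4 | Week 4 scored over 13 items | Week 4 total missing |

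The last two rows are direct contradictions, and the Week 4 row is a possible difference. In both two-visit rows, 8.3.6.1 also calls for carry-forward at the first blank visit, but no donor exists there.

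**4. Size of the Week 4 difference** (illustrations on P)

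- Thirteen items at 3 and one blank: completed-items scoring gives 39/65 = 60.0%. Carrying forward a 1, 3 or 5 gives 40/70 = 57.1%, 42/70 = 60.0% or 44/70 = 62.9%. The gap is at most 2.9 points.
- Seven items at 3 and seven blank (exactly 50%, so not over the limit): completed-items scoring gives 21/35 = 60%. Carry-forward can give anything from 28/70 = 40% to 56/70 = 80%.

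**5. How often the direct contradiction could arise**

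The documents give no blank-item rate. Assume that each item is blank 1% to 3% of the time, independently across items and visits. The chance that at least one of 14 items is blank at both of two consecutive visits is 1 − (1 − 0.01²)^14 = 0.14% to 1 − (1 − 0.03²)^14 = 1.3% per pair of visits. Subjects who keep skipping the same item would raise this.

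**The case against.** The 0–100 may be the intended scale with the subtraction left out of the text, in which case nothing is misreported. It may also be a loose label for a percentage. If the raw sum is what enters the MMRM, the percentage formula does not touch the treatment comparison at all. All of this is possible, and it is why the understatement can only be conditional. It does not remove the need for a single stated formula.

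On blanks, carry-forward in 8.3.6.1 is worded as optional. The section's declared aim is to use the items that were answered and to avoid discarding the whole score, and scoring over completed items fits that aim. This stands for the Baseline-only and Week 2-only cases: the two sections can be read together there. A reader might infer that one blank item at Week 2 leaves the form with no score under 8.3.6.1, and so count every Week 2 form with a blank as lost. The text does not support this. It sets a total to missing only for an item blank at two consecutive visits, or for more than 50% of items blank; for the single blank it is silent.

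The stakes are also low. The endpoint is secondary, without multiplicity control, and SAP 10.1 does not mark its tables (14.2.10.1 and 14.2.10.2) for the top-line package.

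**Conclusion.** The point holds, in limited form, as a minor one.

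The formula as worded and its stated range cannot both be right. If the literal percentage is programmed and reported as 0–100, changes and treatment differences are 0.80 of their value on a true 0–100 scale. A reader might take this to mean that the reported effects will be 20% too small; that follows only under this condition, since the documents do not show which formula or which variable will be programmed. Tests are unaffected by the choice between the two percentage formulas.

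The missing-item rules conflict outright for an item blank at two consecutive visits and can differ for an item blank only at Week 4. The first is probably rare: about 0.1% to 1.3% per pair of visits under the assumed 1–3% independent blank rate. The second shifts a score by up to 2.9 points in the one-blank example.

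A reader might also infer that subjects fall out of the analysis population. SAP 7 defines the mITT population by a Baseline and any post-dose efficacy assessment, not by a complete Q-LES-Q-SF. A missing post-dose total removes that visit from the model, and the subject's other post-dose visit still contributes if available.

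**What to change.** In SAP 8.3.6:

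- Define the analysed score as 100 × (sum − n)/(4n), with n the number of the first 14 items completed, valid if n is at least 7. This delivers the stated 0–100 range, keeps scoring over completed items, and matches the 50% limit already in 8.3.6.1.
- State that this percentage, not the raw sum, is the variable in the MMRM.
- State that this rule takes precedence over 8.3.6.1 for the Q-LES-Q-SF, or remove the scale from 8.3.6.1. Either resolves the conflict.

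Record the clarification of the protocol 9.3.4.2 wording in SAP 2.2, which at present lists only the safety-population change. The cost is a few sentences in the SAP and a check that the derivation program matches. No data collection or design change is needed. It is best settled before unblinding, because the missing-item choice can alter estimates.

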#### 8.3.6.1 Handling of Missing Items Within a Clinical Assessment

The final scores of the Q-LES-Q-SF, QIDS-SR and SDS are all constructed from multiple sub-questions within each assessment. It is possible that one or more sub-questions may be missing within each assessment. In this event, the last recorded score for this sub-question(s) may be carried forward from the most recent post-dose visit (Last Observation Carried Forward approach). In a similar fashion, missing baseline values may be carried over from the most recent screening visit, if available. Baseline/screening values will never be carried forward to impute missing post-dose values. An individual sub-question will not be carried forward for more than one visit. If the same sub-question is missing two visits in a row, then LOCF will be applied to the first missing visit and the sub-question will remain as missing for the second visit (with the total score to then be computed as missing). Further, the total score will be computed as missing if too many sub-questions, prior to applying the LOCF approach, are missing (>50%). This single imputation approach allows the total score to be calculated using the strength of the other sub-questions collected at that time, for that subject. The Sponsor believes this approach to be more accurate than either setting the entire score to missing or to imputing the worst possible score.

#### 8.3.7 Safety Evaluations

The following are all safety evaluations for this study:

- Adverse Events (AEs)
- Clinical safety laboratory tests (serum chemistry [including thyroid function], hematology, coagulation, and urinalysis tests)
- Vital signs (blood pressure, pulse rate, and oral body temperature)
- Body weight
- 12-lead ECGs
- Physical examinations
- C-SSRS

#### 8.3.7.1 Safety Analyses

All summaries of safety and tolerability will be performed on the safety population.

Laboratory parameters, vital sign data, and ECG results will be summarized by treatment group and presented in tabular and graphic formats where appropriate. Appropriate change from Baseline calculations for the mean change from baseline within each treatment group where appropriate will be used for laboratory parameters, vital sign values, ECG results, and C-SSRS results, but no formal statistical tests are planned.

Form STAT401.V3 Page 15 of 23

Client/Project	Arrivo/Sirtsei 201
Version and Date	V01 August 26, 2022

Shift tables will also be provided for laboratory parameters.

Unscheduled and Repeat safety assessments will be listed but will not be summarized in the tabular summaries. Local laboratory results will be listed but will not be summarized in the tabular summaries.

#### 8.3.7.2 Adverse Events

An AE is any untoward medical occurrence in a clinical study subject, whether or not the event is considered causally related to the study drug. An AE can be a new occurrence or an existing process that increases significantly in intensity or frequency.

All Aes must be recorded in the appropriate section of the CRF.

Adverse event monitoring for each subject begins upon Screening and continues until study completion. Abnormalities present at Screening are considered AEs only if they reoccur after resolution or worsen in intensity or frequency during the study. The events recorded with a start date and time on or after the date and time of the first dose of study drug will be considered Treatment Emergent Aes (TEAEs). Each AE is to be classified as serious or non-serious, and categorized with respect to relationship to study drug, and intensity.

Summaries of the number and percentage of subjects in the safety population with at least one treatment-emergent AE (TEAE), classified according to preferred term and/or body system using the MedDRA dictionary, will be provided overall and by treatment group for:

- Overall summary
- All TEAEs
- TEAEs by relationship (not related, possibly related, probably related)
- TEAEs by severity (mild, moderate, severe)
- SAEs
- TEAEs leading to withdrawal from the study
- TEAEs leading to study drug dose reduction
- TEAEs leading to study drug dose taken with food
- Analyses of Aes with time of onset beginning 24 hours after the final dose through up to 28 days after the final dose.

In addition, a summary will be provided of the number and percentage of subjects in the safety population with at least one pre-treatment AE (i.e., Aes with date and time of onset prior to the first dose of study drug).

Listings of events leading to discontinuation or death will be provided.

No formal statistical tests are planned for AE data.

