8. ADVERSE EVENTS, SERIOUS ADVERSE EVENTS, AND OTHER REPORTABLE EVENTS

8.1. Adverse Events

An AE is any untoward medical occurrence in a clinical study subject, whether or not the event is considered causally related to the study drug. An AE can be a new occurrence or an existing process that increases significantly in intensity or frequency.

All AEs must be recorded in the appropriate section of the CRF.

Adverse event monitoring for each subject begins upon Screening and continues until study completion. Abnormalities present at Screening are considered AEs only if they reoccur after resolution or worsen in intensity or frequency during the study.

Each AE is to be classified as serious or non-serious, and categorized with regard to relationship to study drug, and intensity.

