8.1.1. Clinical Safety Assessment Abnormalities

Abnormal findings on clinical safety assessments, including clinical safety laboratory test results, vital sign measurements, ECGs, and physical examinations, will be assessed by the Investigator as clinically significant or not clinically significant. Clinically significant abnormalities that are new or exacerbate after the Screening Visit will be reported as AEs. Classification of seriousness, relationship to study drug, and intensity should use the guidelines provided in Section 8.1.2, Section 8.1.4.3 and Section 8.1.4.4, respectively.

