8.1.4.2. Date and Time of Adverse Event Onset and Resolution

The time, if available, and date at which the AE was first apparent will be recorded as the event onset. The date and time of onset of symptoms may be appreciably earlier than the date and time the Investigator becomes aware of the event. Some events may be apparent to the subject and Investigator independently, and information from each may contribute to the final report. The date and time of resolution of the event will be recorded when they are available.

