#### 6 Visit Schedule and Visit Windows

A Screening period of up to 28 days (Day -28 to Day -2) and a Baseline Visit (Day -1) will precede initiation of the Treatment Period. During the Screening Period, all Screening assessments will be completed, and any current depression medications will be discontinued. All Screening assessments should be completed before discontinuing any current depression medications. Subjects who continue to satisfy all entry criteria at the Baseline Visit will be randomized in a 1:1 ratio to one of the two treatment groups. At the completion of the Baseline Visit, randomized subjects will be dispensed study drug and will be instructed to begin dosing the next morning (Day 1).

During the Treatment Period, subjects will be scheduled to return to the clinic for safety and efficacy assessments at the end of Weeks 1, 2, 3, and 4 as specified in the SOE (Table 2 of the protocol). After the final dose of study drug, subjects will complete a Follow-up Period of two weeks and will return at the end of Week 5 (1 week after final dose) and Week 6 (2 weeks after final dose). Subjects may be treated with anti-depressant medications according to physician recommendations after completion of the Week 5 Visit unless a clinically significant lab value is identified at the Week 4 Visit. If a clinically significant lab value is identified at the Week 4 Visit. If a clinically significant lab value needs to be followed prior to initiating new therapy. Unless there are any outstanding safety issues that require follow-up, subjects will be discharged from the study at the Week 6 Visit.

Form STAT401.V3 Page 6 of 23

Client/Project	Arrivo/Sirtsei 201
Version and Date	V01 August 26, 2022

Table 6.1, Sirtsei 201 Study Visit Schedule

Study Period	Screening/ Washout	Baseline		Treatment Period	nt Period		Follow-up Period	p Period
Study Visit	-	2	3	4	w	9	7	8
			Week 1	Week 2	Week 3	Week 4 / Premature D/C	Week 5/ 1-Week Follow-up (7±3 days	Week 6/ 2-Week Follow-up (14 ± 3
Study Day / Week	Day -28 to -2	Day -1	(Day 7±3 Days)	(Day 14±3 Days)	(Day 21±3 Days)	(Day 28±3 Days)	post last dose)	days post last dose)
Event / Assessment								
Clinic Visit 	X	X	X	X	X	X	X	X
Informed Consent	X							
Inclusion/Exclusion	X	X						
Diagnosis Confirmation	X							
and Treatment History								
Height and Weight 	X	X				X		
Physical Exam 	X	X	X	X	X	X	X	
C-SSRS 	X	X	X	X	X	X	X	X
Pregnancy Test 	X	X				X		

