**Table 8.1, Handling of Intercurrent Events** 

Estimand	Intercurrent Event	Rule / Rationale
Primary	Premature discontinuation /	Hypothetical "as own treatment" strategy. Clinical
	Permanent treatment	course is the same as other subjects in the same
	discontinuation	treatment group, who had not discontinued study
		treatment.
		Exclude observations that occur more than 3 days
		after the last dose of study drug for subjects who
		discontinue. The objective of the study is to
		evaluate the effect of SP-624 subjects who are
		provided drug to take on a standard schedule up to 4
		weeks. After 3 days, the drug should be cleared
		from all subjects, so the inclusion of any such data
		point is inconsistent with the goal of the estimand.
	Drug non-compliance / Missed	Treatment policy strategy.
	study medication	Some degree of non-compliance missed doses
		would be expected to occur in standard use.
	Protocol deviations not leading	Treatment policy strategy
	to study discontinuation	Overall, if not sufficient to lead to subject removal,
		the expectation is that they would not significantly
		impact subject results.
	Concomitant medications in	Treatment policy strategy
	violation of the protocol	This is expected to be a rare event in this clinical
		trial and treatment effect will be estimated
		irrespective of concomitant medication violations.

The hypothetical "as own treatment" strategy was selected for premature discontinuation or treatment discontinuation intercurrent events to evaluate the effect of treatment with respect to its pharmacologic efficacy. For the change from week 4 to week 5 follow-up secondary analysis, only subjects that were included in the week 4 primary analysis will be used. This should provide the most unbiased data for this

Form STAT401.V3 Page 12 of 23

Client/Project	Arrivo/Sirtsei 201
Version and Date	V01 August 26, 2022

phase 2 study to inform future studies. The treatment policy strategy will be used for all other defined intercurrent events.

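### The TEAE rule looks only at recorded start date, so worsening on drug of a washout AE is classified by site recording practice, and onsets after a new antidepressant are not distinguished

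*SAP*

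**What the plan says.** The TEAE rule in SAP 8.3.7.2 is "The events recorded with a start date and time on or after the date and time of the first dose of study drug". It has no clause for worsening of an earlier event and no last day. The protocol uses the term in 9.3.9.1 but does not define it.

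Four other provisions determine how the rule works:

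- **Collection.** AE monitoring runs from Screening to study completion (Protocol 8.1, SAP 8.3.7.2). Current depression medication is stopped during the Screening Period (SAP 6).
- **Onset.** Protocol 8.1.4.2: "The time, if available, and date at which the AE was first apparent will be recorded as the event onset".
- **Worsening.** SAP 8.3.7.2: "An AE can be a new occurrence or an existing process that increases significantly in intensity or frequency". For safety assessments, Protocol 8.1.1 adds: "Clinically significant abnormalities that are new or exacerbate after the Screening Visit will be reported as AEs".
- **After dosing.** SAP 6: "Subjects may be treated with anti-depressant medications according to physician recommendations after completion of the Week 5 Visit", subject to a check on Week 4 laboratory values. For efficacy, SAP Table 8.1 excludes late observations on the ground that "After 3 days, the drug should be cleared".

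SAP 8.3.7.2 also plans a summary of AEs with onset before the first dose. A further summary covers onsets from 24 hours to 28 days after the final dose (Table 14.3.1.10).

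**The concern.** The TEAE tables are the main output for the secondary safety and tolerability objective. In SAP 10.1 the tables by relationship, severity, seriousness, study withdrawal and dose reduction (14.3.1.3 to 14.3.1.8) are all restricted to treatment-emergent events. An event that misses the TEAE definition misses all of them.

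The washout makes this a practical matter, because stopping an antidepressant can be expected to produce some symptom AEs shortly before the first dose. If one of these becomes severe on study drug, a safety reviewer would want it in the treatment-emergent severity table. Whether it gets there depends on how each of about 40 sites enters the worsening.

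At the other end, an event that begins after a non-study antidepressant is started carries the same label as an event on SP-624 or placebo.

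**Working it through.** The plan gives no figure on this point. The check is a comparison of texts, followed by day counts from the visit schedule.

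**Start of the window.** Take nausea first apparent on Day -10, recorded as an AE, that becomes severe on Day 5.

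1. Under Protocol 8.1.4.2 the original record keeps its Day -10 onset.
2. Under the SAP rule, Day -10 is before the first dose, so that record is a pre-treatment AE.
3. If the site enters the worsening as a separate AE, its onset is Day 5 and it is a TEAE. The AE definition permits this.
4. No text requires it for this case. The worsening sentence in Protocol 8.1 concerns abnormalities already present at Screening. Protocol 8.1.1 concerns laboratory, vital sign, ECG and physical examination findings. A symptom AE that arises during washout falls under neither.

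The classification is therefore conditional on an unstated recording rule.

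**End of the window.** Inputs: the Week 4 Visit and last dose are taken at Day 28. Week 5 is 7 ± 3 days and Week 6 is 14 ± 3 days after the Week 4 Visit (Protocol 7.1). Clearance is 3 days (SAP Table 8.1). AE collection is taken to end at Week 6.

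| Schedule | Week 5 / Week 6 (days after Week 4) | TEAE days | After last dose | After 3-day clearance | After Week 5 |
|---|---|---|---|---|---|
| Nominal | 7 / 14 | 28 + 14 = 42 | 14 (14/42 = 33%) | 14 - 3 = 11 (11/42 = 26%) | 14 - 7 = 7 (7/42 = 17%) |
| Shortest | 10 / 11 | 28 + 11 = 39 | 11 (11/39 = 28%) | 11 - 3 = 8 (8/39 = 21%) | 11 - 10 = 1 (1/39 = 3%) |
| Longest | 4 / 17 | 28 + 17 = 45 | 17 (17/45 = 38%) | 17 - 3 = 14 (14/45 = 31%) | 17 - 4 = 13 (13/45 = 29%) |

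The half-lives in Protocol 2.2.3.1 (6.8 to 7.1 hours) agree with the clearance statement: 72/7.1 = 10.1 and 72/6.8 = 10.6 half-lives.

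Two variations:

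- **Early stopper.** If the last dose and the Premature Discontinuation Visit are both on Day 7, follow-up nominally ends on Day 21, and (14 - 3)/21 = 52% of the window is after clearance.
- **SAEs.** These are recorded to 28 days after the Week 4 Visit (Protocol 8.1.2), so for a completer the share is (28 - 3)/56 = 45%.

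These are shares of time, not of events. The documents give no AE rates by arm or period, so neither the number of washout events that worsen on drug nor the effect on a between-arm comparison can be calculated.

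**The case against.** The best defence is that the AE definition already treats a significant increase in an existing process as an AE. Its onset is then the date the increase was first apparent, which is after the first dose. This stands as a permitted reading, and it is why a reader should not infer that such events are certainly left out. It does not make the reading an instruction.

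Several further points stand:

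- Washout insomnia or low mood would be a poor example, because Protocol 8.1.4 keeps symptoms of MDD out of the AE record. The gap concerns other symptoms.
- The events do not vanish. Listing 16.3.1 shows all AEs, SAP 8.3.7.2 plans listings of events leading to discontinuation or death, and disposition gives withdrawal reasons. A pre-treatment summary is also planned, although SAP 10.1 names no separate table for it. A reader might infer that drug effects are hidden; the documents support only that they may be missing from the main tables.
- Collection does end, at Week 6 for AEs. Post-dose onsets have Table 14.3.1.10, and follow-up medications are summarised by arm (SAP 8.3.3.1). These onsets are nevertheless not removed from, or marked in, the TEAE tables.
- Counting follow-up events as TEAEs keeps delayed and withdrawal effects in view. The 3-day statement supports the efficacy estimand and is not offered as a safety cut-off. A reader might want TEAEs to stop there, but that would take later SAEs out of the serious, severity and relationship tables, and Table 14.3.1.10 is not described as split in those ways.
- A reader might infer that the arms are pulled together by a known amount. Any such figure needs assumed event rates, and withdrawal effects on SP-624 could act the other way.

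**Conclusion.** The point holds as a gap in classification. For a symptom AE that starts in washout and worsens on drug, entry to the TEAE tables depends on whether the site opens a new record, and neither document settles this. Separately, the tables mix on-drug events with post-dose events and with events that follow a newly started antidepressant. On the nominal schedule the last of these can arise in 7 of 42 days (1 to 13 days across the visit windows), and 11 of 42 days (26%) lie beyond the SAP's clearance point. The day counts assume dosing up to a Day 28 Week 4 Visit.

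The same rule applies to both arms and no formal AE tests are planned. The consequence is misclassification and possible dilution of the on-drug picture, of unknown size and direction, not a demonstrated bias. It should be corrected because the correction is simple and the affected tables carry the safety objective.

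**What to change.** 1. **SAP 8.3.7.2.** Define a TEAE as an AE that starts on or after the first dose, or an AE with earlier onset that increases in intensity or frequency or becomes serious on or after the first dose. Because onset time is recorded only when available, add a rule for Day 1 onsets with no time.
2. **Recording.** Have such worsening entered as a new AE with its own onset date. The SAP is dated August 2022 and the protocol expected the last visit in November 2021, so collection may be over. In that case, identify candidates in the Safety Population from existing fields: AEs with pre-dose onset that are serious, or whose action taken is discontinuation, dose reduction or dosing with food. This may miss changes in intensity alone, and the SAP should say so.
3. **Post-dose events.** Keep them in the TEAE tables. Flag, or show separately, onsets after the last dose and onsets after the start of a non-study antidepressant. Do not impose a 3-day cut-off.

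The cost is SAP wording and minor programming. A few events move from the pre-treatment summary to the TEAE tables; none leaves reporting.
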